5.8 Criteria for Taking a Participant Off Study

Participants will be removed from study when any of the following criteria apply:

- Lost to follow-up
- Withdrawal of consent for data submission
- Death

The reason for taking a participant off study, and the date the participant was removed, will be documented in the case report form (CRF).

6. BIostatistical Analysis

6.1 Study design/Endpoints

The primary objective of this open label randomized phase II study is to evaluate the efficacy and tolerability of topical compound dexamethasone solution in a Mucolox™ for the treatment of oral lichen planus. The primary endpoint will be a change from pre to post treatment in each subject's subjective sensitivity score (0-10) evaluated at baseline and 4 weeks post treatment for each arm. We will also compare changes of the daily subject's subjective sensitivity score (0-10) over time for each arm.

The secondary objectives include the evaluation of objective data using the REU scoring system and the oral health related quality of life using the 24-item Chronic Oral Mucosal Diseases Quality of Life Questionnaire. For the analysis of secondary endpoints see section 6.5.

6.2 Sample Size, Accrual Rate and Study Duration

The sample size was calculated based on the data by Rhodus et al., as to ensure at least 80% power and two-sided alpha of 0.05 in detecting a t difference of 2.0 points oral pain on an 11 point scale (VAS 0-10) between Arm A and B²⁴. The mean expected change for Arm A will be 6.5 points reduction with a standard deviation of 1.4 points. The mean expected change for Arm B will be 4.5 points reduction with a standard deviation of 1.4 points.

A total of 12 patients per arm will be enrolled (total of 24 subjects). The proposed sample size includes a loss of follow up of 5%. Approximately 75 patients per year are diagnosed with oral lichen planus at the Division of Oral Medicine and Dentistry (BWH)³². We anticipate the accrual rate will be approximately 5 patients per month, thus the accrual goal will be achieved in approximately five months.

6.3 Interim Monitoring Plan

Involvement in this study as a participating investigator implies acceptance of potential audits or inspections, including source data verification, by representatives designated by BWH or the BWH

CONFIDENTIAL

This document is confidential. Do not disclose or use except as authorized.

Overall Principal Investigator. The purpose of these audits or inspections is to examine study-related activities and documents to determine whether these activities were conducted and data were recorded, analyzed, and accurately reported in accordance with the protocol, institutional policy, Good Clinical Practice (GCP), and any applicable regulatory requirements.

All data will be monitored for timeliness of submission, completeness, and adherence to protocol requirements. Monitoring will begin at the time of participant registration and will continue during protocol performance and completion

6.3.1 Monitoring of Adverse Events

All adverse events will be reviewed by the principal investigator or covering clinician. In accordance with PHRC guidelines, the PI or covering clinician will determine whether an adverse event was expected and/or related to study procedures. Study subjects will be asked to report any adverse events or concerns to study staff as they arise.

6.3.2 Protocol Review and Amendments

This protocol, the proposed informed consent and all forms of participant information related to the study (e.g., advertisements used to recruit participants) and any other necessary documents will be submitted, reviewed and approved by a properly constituted IRB governing each study location.

Any changes made to the protocol will be submitted as amendments and will be approved by the IRB prior to implementation. Any changes in study conduct will be reported to the IRB. The BWH Overall Principal Investigator will disseminate protocol amendment information to all participating investigators.

All decisions of the IRB concerning the conduct of the study will be made in writing.

6.4 Analysis of Primary Endpoints

VAS scores will be summarized descriptively for each arm at pre-treatment, post-treatment, and pre-to-post treatment change. The pre-to-post treatment change will be compared between the arms using either Student's t-test or Mann-Whitney test, depending on the distribution of the data.

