1.2 Dexamethasone solution for oral lichen planus

The efficacy of dexamethasone solution has been well described in several clinical trials. Rhodus et al. conducted a prospective controlled clinical trial to test the efficacy of dexamethasone solution in 13 patients with oral erosive-ulcerative lichen planus²⁴. Patients were instructed to rinse with 5 ml of dexamethasone 0.1% solution for 3 min and then to expectorate. Subjective symptomatology (pain and/or discomfort) was recorded on a 100 mm visual analogue scale (VAS) at first visit and at 6 week follow up. Patients experienced significant subjective improvement in symptoms following the dexamethasone treatment (VAS score pre-treatment: 6.7 ± 1.4 ; VAS score post-treatment: 2.3 ± 0.6). Hambly et al. conducted a single-blinded, cross-over pilot trial in nine patients to compare the efficacy of compounded dexamethasone solution for OLP²⁵. Patients were instructed to rinse with 2 ml of dexamethasone 0.5 mg/2 mL compounded as a solution or one 0.5 mg tablet crushed and mixed with 20 ml water three times per day for 3 weeks. All patients were instructed to rinse and hold the medication in their mouths for at least 2–3 minutes and then expectorate. Participants were evaluated at weeks 0, 3, 4, and 7. Symptoms were recorded with a 100-mm VAS; other assessments included the Treatment Satisfaction Questionnaire for Medication-9, comparisons of clinical photographs, and self-assessment via patient daily diary entries to record compliance with each dose. Results showed the compounded dexamethasone solution to be more effective compared to 0.5 mg dexamethasone tablet crushed and mixed with 20 ml water in terms of compliance, patient-perceived faster onset of action, and improved symptom relief.

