2.1 Study Design

This is a single center, 4-week, open label randomized, phase II study. Randomization will be conducted by the BWH Investigational Pharmacy. The study period will be four weeks, which based on previous studies should be an adequate period to assess significant clinical improvement. Subjects will be evaluated clinically at baseline before starting treatment and at the end of the four-week period, for a total of two visits. Subjects will be randomized to either compound dexamethasone in Mucolox™ or dexamethasone only. Subjects will return for evaluation after four weeks at which time the primary end-points will be assessed.

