3. SUBJECT SELECTION

3.1 Eligibility Criteria

- 3.1.1 Age 18 years and older.
- 3.1.2 Patients with symptomatic oral lichen planus (worst VAS sensitivity score ≥ 7 over the last week).
- 3.1.3 Ability to understand and the willingness to sign a written informed consent document.

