6.5 Analysis of Secondary Endpoints

Oral health related quality of life will be assessed before and after topical therapy using the 24-item Chronic Oral Mucosal Diseases Quality of Life Questionnaire (COMDQLQ; see Appendix) instrument that measures subject's perceptions of the impact of oral conditions on their well-being. The COMDQLQ scores will be summarized descriptively for each arm at pre-treatment, post-treatment, and pre-to-post treatment change. The pre-to-post treatment change for each item and for all items combined will be assessed within each arm using either paired t test or Wilcoxon-signed-rank test depending on its distribution. In addition, each question will be dichotomized and classified as 'response' if the answer is 'not at all', or 'slightly' to a question such as "how isolated do you feel as a

CONFIDENTIAL

This document is confidential. Do not disclose or use except as authorized.

result of this oral condition”, and pre-to-post treatment improvement will be assessed using McNemar’s test within each arm.

In order to evaluate the clinical improvement in clinician-reported outcome measures for oral lichen planus, REU scores within the compound dexamethasone solution in Mucolox™ group (Arm A) will be compared to that in the dexamethasone solution only group (Arm B). The REU scores will be summarized descriptively for each arm at pre-treatment, post-treatment, and pre-to-post treatment change. The pre-to-post treatment change will be compared between the arms using either student’s t-test or Mann–Whitney test, depending on the distribution of the data.

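### Section 6.4 leaves the primary test to be picked from the outcome data without a rule and does not adjust for baseline; naming one ANCOVA would settle both

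*Combined protocol and SAP*

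**What the plan says.** Section 6.1 defines the primary endpoint as the change in each subject's 0-10 sensitivity score, "evaluated at baseline and 4 weeks post treatment for each arm". Section 6.4 is the whole primary analysis: scores are described by arm before treatment, after treatment and as change, and the change is then "compared between the arms using either Student's t-test or Mann-Whitney test, depending on the distribution of the data". It names no normality test, threshold, decision-maker or time of decision. Baseline enters only through the subtraction and the descriptive summary.

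Section 6.5 has the same either/or plan for the REU score. Section 6.2 sizes the trial on a difference in mean change of 2.0 points. For the control arm it states: "The mean expected change for Arm B will be 4.5 points reduction with a standard deviation of 1.4 points". Arm A is given a 6.5-point reduction with the same SD. Section 2.1 describes the design: "This is a single center, 4-week, open label randomized, phase II study". The visit forms in Appendices 3 and 4 both record worst sensitivity over the last week, so the baseline value is already collected.

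**The concern.** There are two gaps, and one sentence can close both.

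**The test is open.** A t-test addresses a difference in means; Mann-Whitney addresses a shift in ranks. The trial is powered on a mean difference, but if the rank test is chosen, section 6.4 requires no between-arm mean difference or confidence interval. In an open-label trial the distribution would be inspected by people who may know the arms.

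**Baseline is only subtracted.** Analysing raw change fixes the slope of week-4 score on baseline at 1. If the true slope is below 1, the arm that happens to start higher shows a larger fall for reasons unrelated to treatment. With 12 per arm, such an imbalance can be a visible part of a 2.0-point effect.

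**Working it through.** **Inputs from the document.** Section 6.2: 12 per arm, SD of change 1.4, difference 2.0, two-sided alpha 0.05, at least 80% power, 5% loss. Section 1.2, planning source: pre-treatment 6.7 ± 1.4; "VAS score post-treatment: 2.3 ± 0.6". Section 3.1, entry: "worst VAS sensitivity score ≥ 7 over the last week".

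**Assumed, because the document does not give them.** Baseline SD, and pre/post correlation r (shown from 0 to 0.5).

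**1. The plan's own sample size.** The t-test (noncentral t) needs 9 per arm (power 81.2%), or 9/0.95, rounded up to 10, after loss. The stated 12 is reproduced if the t-test figure is divided by the worst-case Mann-Whitney efficiency: 9/0.864, rounded up to 11, then 11/0.95, rounded up to 12. No formula is named, so this route is an inference. At 12 per arm, SE = 1.4 × √(2/12) = 0.572, noncentrality = 2.0/0.572 = 3.50 on 22 df, and power is 91.7%. At 1.5 points it is 70.8%.

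**2. Chance imbalance.** A normal (6.7, 1.4) truncated to 7-10 has mean 7.96 and SD 0.70. SE of the baseline difference = 0.70 × √(2/12) = 0.286, so the 95% range is ±1.96 × 0.286 = ±0.56. If scores were instead spread evenly over 7, 8, 9 and 10, the SD would be √1.25 = 1.12 and the range ±0.89.

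**3. Shift and power, holding the SD of change at 1.4.** With s0 = 0.70:
- Post-treatment SD: s1 = r·s0 + √((r·s0)² − s0² + 1.96)
- Slope on baseline: r·s1/s0
- Shift for an imbalance of 0.56: (1 − slope) × 0.56
- ANCOVA variance: s1²(1 − r²), inflated by 1 + 1/(2×12 − 4) = 1.05, on 21 df

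Example, r = 0.2: s1 = 0.14 + √1.4896 = 1.36. Slope = 0.2 × 1.36/0.70 = 0.39. Shift = 0.61 × 0.56 = 0.34. Variance = 1.777 and SE = √(1.777 × 2/12 × 1.05) = 0.558. Noncentrality is 3.59 and power is 92.8%.

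| r | s1 | slope | shift (points) | ANCOVA power, 2.0 | ANCOVA power, 1.5 |
|---|---|---|---|---|---|
| 0 | 1.21 | 0 | 0.56 | 96.4% | 80.5% |
| 0.2 | 1.36 | 0.39 | 0.34 | 92.8% | 72.8% |
| 0.3 | 1.44 | 0.62 | 0.21 | 91.2% | 70.2% |
| 0.4 | 1.52 | 0.87 | 0.07 | 90.4% | 68.7% |
| 0.5 | 1.61 | 1.15 | −0.08 | 90.4% | 68.8% |
| Unadjusted t-test | | | | 91.7% | 70.8% |

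A wider baseline favours ANCOVA more. With equal pre and post SDs and r = 0.3, both SDs are 1.4/√1.4 = 1.18 and power at 2.0 points is 98.0%. That SD is slightly above the even-spread figure of 1.12, so this is an optimistic case.

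**4. Bounded integer scores.** A 6.5-point fall from a mean near 8 leaves about 1.5, close to the floor. Simulated with rounding and a floor (3,000 trials per scenario), power at 2.0 points for the t-test on change versus ANCOVA is 88.0% vs 95.0% (r = 0), 88.4% vs 91.3% (0.2) and 88.4% vs 87.0% (0.5). ANCOVA type I error is 4.8-5.2%.

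**5. The open choice.** Across two sets of simulations (3,000 and 8,000 trials per scenario), the t-test and Mann-Whitney fall on opposite sides of p = 0.05 in 3.5-4.2% of trials at 2.0 points, 5.4-7.7% at 1.5 points and about 2% with no effect. Type I error is about 5% if a normality pre-test decides, and at most about 5.8% if the smaller p-value is taken.

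**The case against.** The strongest reply is that nothing fails. Under 1:1 randomisation the change-score comparison is unbiased, its variance already includes chance imbalance, type I error is close to nominal, and power at the planned difference exceeds the 80% target. This stands, and it is why the point is an improvement and not an error.

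The 0.56-point shift also takes the worst case twice: imbalance at the 95% limit and r = 0. The median absolute imbalance is 0.6745 × 0.286 = 0.19 points, which moves the result by 0.12 at r = 0.2, 0.07 at 0.3 and about 0.03 at 0.4-0.5. That stands too.

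The correlation and baseline SD are assumed, and the sources pull apart. Holding the SD of change at 1.4 implies post-treatment SDs of 1.21 to 1.61, at least twice the planning source's 0.6. With 0.70, 0.6 and r = 0.2, the SD of change is √(0.49 + 0.36 − 0.168) = 0.83. Power at 2.0 points then exceeds 99.9% with either method; ANCOVA's advantage (81% to 97%) appears only at a 1.0-point difference, which the trial does not plan for.

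It can also be said that the endpoint is fixed and change will be described by arm whichever test is used. True, but per-arm summaries are not a pre-stated between-arm estimate with an interval.

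Finally, stating a selection rule or naming one test would close the first gap without ANCOVA. It would, but it would leave baseline unadjusted. Neither remedy addresses the post-randomisation exclusions and replacements in section 6.6, which are a separate matter.

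**Conclusion.** The point holds, as a low-cost improvement to consider. Two facts rest on the text alone: section 6.4 has no rule for choosing the test, and no analysis in the document uses baseline as a covariate. The consequences are moderate. An imbalance at the 95% limit shifts the primary comparison by up to 0.56 points, or 0.34 at r = 0.2, which is 17% of the planned difference. The choice of test changes the significance call in about 4% of trials at 2.0 points.

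The case for ANCOVA is protection against imbalance and one estimate, interval and p-value fixed in advance. It is not a promised gain in power: on the plan's SD of change and a baseline SD of 0.70, the effect at 2.0 points runs from about −1 to +5 percentage points. These sizes depend on the assumed correlation and baseline SD, so confidence in them is medium; confidence in the two textual gaps is high.

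**What to change.** Replace the comparison sentence in section 6.4 with:

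> The primary analysis is ANCOVA of the week-4 worst-sensitivity score on arm and baseline worst-sensitivity score. The adjusted difference (Arm A minus Arm B) is reported with its 95% CI and two-sided p-value. The Mann-Whitney test of the pre-to-post change is a sensitivity analysis and does not replace the primary result.

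The same model can serve for REU in section 6.5, though the document gives no REU SD or correlation from which to size the benefit.

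Cost: wording only, with no new data and no change from 24 patients. Because section 6 is part of the protocol, section 6.3.2 requires an amendment with IRB approval; it should be made before outcome data are examined. The statistical price is one degree of freedom: a loss of about 1 percentage point of power at 2.0 points and about 2 at 1.5 points if the correlation is 0.4-0.5.

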6.5 Analysis of Secondary Endpoints

Oral health related quality of life will be assessed before and after topical therapy using the 24-item Chronic Oral Mucosal Diseases Quality of Life Questionnaire (COMDQLQ; see Appendix) instrument that measures subject's perceptions of the impact of oral conditions on their well-being. The COMDQLQ scores will be summarized descriptively for each arm at pre-treatment, post-treatment, and pre-to-post treatment change. The pre-to-post treatment change for each item and for all items combined will be assessed within each arm using either paired t test or Wilcoxon-signed-rank test depending on its distribution. In addition, each question will be dichotomized and classified as 'response' if the answer is 'not at all', or 'slightly' to a question such as "how isolated do you feel as a

CONFIDENTIAL

This document is confidential. Do not disclose or use except as authorized.

result of this oral condition”, and pre-to-post treatment improvement will be assessed using McNemar’s test within each arm.

In order to evaluate the clinical improvement in clinician-reported outcome measures for oral lichen planus, REU scores within the compound dexamethasone solution in Mucolox™ group (Arm A) will be compared to that in the dexamethasone solution only group (Arm B). The REU scores will be summarized descriptively for each arm at pre-treatment, post-treatment, and pre-to-post treatment change. The pre-to-post treatment change will be compared between the arms using either student’s t-test or Mann–Whitney test, depending on the distribution of the data.

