3.2 Exclusion Criteria

- 3.2.1 Patients already on topical or systemic steroids.
- 3.2.2 Inability to comply with study instructions.
- 3.2.3 Uncontrolled intercurrent illness or psychiatric illness/social situations that would limit compliance with study requirements.
- 3.2.4 VAS sensitivity score < 7 .
- 3.2.5 Pregnant women. A urine pregnancy test will be performed for women of child bearing potential.

CONFIDENTIAL

This document is confidential. Do not disclose or use except as authorized.

3.2.6 Allergy to fluconazole, clotrimazole or nystatin.

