5.1.2 Chronic Oral Mucosal Diseases Quality of Life Questionnaire

Patients will complete the 24-item Chronic Oral Mucosal Diseases Quality of Life Questionnaire (COMDQLQ) instrument at baseline and at the end of treatment³¹. This is a validated instrument that assesses various aspects of oral health and function that has been shown to perform well in patients with oral mucosal diseases, including oral lichen planus.

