8. Rate the taste of the topical treatment:

[figure not shown]
[figure not shown]

Very good taste

Very bad taste

Score: _____

9. Rate how your mouth feels since starting topical therapy:

Mouth feels much better

Mouth feels much worse

Score: _____

10. Overall, since beginning topical therapy, my mouth is: (Check one)

- Very much better
- Moderately better
- A little better
- About the same
- A little worse
- Moderately worse
- Very much worse

CONFIDENTIAL

This document is confidential. Do not disclose or use except as authorized.

OBJECTIVE DATA

Site	Reticular area			Erythematous area			Ulcerative area			
	0	1	0	1	2	3	0	1	2	3
Upper/lower labial mucosa	0	1	0	1	2	3	0	1	2	3
Right buccal mucosa	0	1	0	1	2	3	0	1	2	3
Left buccal mucosa	0	1	0	1	2	3	0	1	2	3
Dorsal tongue	0	1	0	1	2	3	0	1	2	3
Ventral tongue	0	1	0	1	2	3	0	1	2	3
Floor of mouth	0	1	0	1	2	3	0	1	2	3
Hard palate mucosa	0	1	0	1	2	3	0	1	2	3
Soft palate/tonsillar pillars	0	1	0	1	2	3	0	1	2	3
Maxillary gingiva	0	1	0	1	2	3	0	1	2	3
Mandibular gingiva	0	1	0	1	2	3	0	1	2	3
Total										

(R: 0 = not present, 1 = present; E & U: 0 = not present, 1 = <1cm², 2 = 1 - 3cm², 3 = >3cm²)

Total Score:

Total Weighted Score:

PHOTOGRAPHS TAKEN (circle): YES NO

CONFIDENTIAL

This document is confidential. Do not disclose or use except as authorized.

COMDQLQ

	Not at all (0)	Slightly (1)	Moderately (2)	Considerably (3)	Extremely (4)
Pain and functional limitation					
How much do certain types of food/drink cause you discomfort (spicy food, acidic food)?					
How much does your oral condition cause you to limit the types of food/ drinks you consume?					
How much do certain food textures cause you discomfort (rough food, crusty food)?					
How much does your oral condition cause you to limit the textures of the food you consume?					
How much does the temperature of certain foods/drinks cause you discomfort?					
How much does your oral condition cause you to limit the temperature of the foods/ drinks you consume?					
How much does your oral condition lead to discomfort when carrying out your daily oral hygiene routine (brushing, flossing, mouthwash usage)?					
How much does your oral condition cause you to limit your daily oral hygiene routine (brushing, flossing, mouthwash usage)?					
How much does your oral condition lead to discomfort when wearing a denture (false teeth)?					
Medication and treatment					

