How much do you feel you need medication to help you with activities of daily life (talking, eating, etc.)?					
How satisfied are you with the medication being used to treat your oral condition?					
How concerned are you about the possible side effects of the medications used to treat your oral condition?					
How much does it frustrate you					

CONFIDENTIAL

This document is confidential. Do not disclose or use except as authorized.

that there is no single standard medication to be used in your oral condition?					
How much does the use of the medication limit you in your everyday life (routine/the way you apply or take your medications)?					
How much does it bother you that there is no cure for your oral condition?					
Social and emotional					
How much does your oral condition you down?					
How much does your oral condition cause you anxiety?					
How much does your oral condition cause you stress?					
How much does the unpredictability your oral condition bother you?					
How much does your oral condition cause you to worry about the future (spread of the condition, possible cancer risk)?					
How much does your oral condition make you pessimistic about the future?					
How much does your oral condition disrupt social activities in your life (social gatherings, eating out parties)?					
Patient support					
How satisfactory do you consider the information available to you regarding your oral condition?					
How satisfied are you with the level of support and understanding shown to you by family regarding this oral condition?					
How satisfied are you with the level of support and understanding shown to you by friends/work colleagues regarding your oral condition?					
How isolated do you feel as a result of this oral condition?					

CONFIDENTIAL

This document is confidential. Do not disclose or use except as authorized.

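### Within-arm pre-to-post tests of three COMDQLQ medication items mix the start of a rinse with change in disease, no between-arm COMDQLQ test is planned, and the stated 24 items do not match the 26 printed

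*Combined protocol and SAP*

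**What the plan says.** Section 5.1.2 sets the timing: "Patients will complete the 24-item Chronic Oral Mucosal Diseases Quality of Life Questionnaire (COMDQLQ) instrument at baseline and at the end of treatment". Section 5 places the baseline visit ahead of any study treatment. Section 6.5 then sets the analysis: "The pre-to-post treatment change for each item and for all items combined will be assessed within each arm using either paired t test" or the Wilcoxon signed-rank test. Each question is also dichotomised, with 'not at all' or 'slightly' counted as response, and tested by McNemar's test within each arm. Section 6.5 gives a between-arm test for the REU score but none for the COMDQLQ, which is otherwise only summarised by arm.

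Section 3.2.1 excludes "Patients already on topical or systemic steroids". Both arms then start a 5-minute rinse three times a day (5.2).

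The medication block of the form in Appendix 5 includes "How satisfied are you with the medication being used to treat your oral condition" and "How much does the use of the medication limit you in your everyday life (routine/the way you apply or take your medications", and a further item on concern about possible side effects. Sections 5.1.2, 6.1 and 6.5 all describe the instrument as having 24 items.

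**The concern.** A change score needs the question to mean the same thing at both visits. For a patient on no treatment for oral lichen planus at visit 1, the satisfaction and limits items have nothing clear to refer to. At visit 2 they refer to the study rinse. The side-effect item is a partial case, because a patient can hold a view on possible side effects before the first dose. The plan has no rule for a 'not applicable' answer.

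A significant within-arm change on one of these items could therefore be reported as a gain or loss in quality of life when part or all of it reflects only that treatment began. The same change enters the all-items total. Both arms start a rinse, so a comparison between arms would largely remove this component, but that comparison is not planned. The question the trial asks, Arm A against Arm B, is the one these items could inform at week 4.

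A smaller point is that the reader cannot tell which items make up the total.

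**Working it through.** **1. Item count (Appendix 5).** Questions by block, with the one split by a page break counted once:

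- Pain and functional limitation: 9
- Medication and treatment: 6
- Social and emotional: 7
- Patient support: 4

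Total: 9 + 6 + 7 + 4 = 26, against the stated 24. The first is "How much do certain types of food/drink cause you discomfort (spicy food, acidic food" and the last is "How isolated do you feel as a result of this oral condition". Each is scored 0 to 4, so the maximum total is 26 × 4 = 104. Twenty-four items would give 24 × 4 = 96. The documents state neither maximum and do not show which 24 items were meant.

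**2. Items affected.** Three of the six medication items concern medication in use: satisfaction, side-effect concern and limits on daily life. They carry 3 × 4 = 12 of 104 points. The other three (need for medication, no single standard medication, no cure) can be answered at baseline.

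**3. The limits item under McNemar's test.** An untreated patient who answers 'not at all' (0) at visit 1 is at the floor and can only stay there or worsen. Let b be the number moving from response to non-response, with none moving back. The exact two-sided p is 2 × 0.5^b:

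- b = 5: 2 × 0.5^5 = 0.0625
- b = 6: 2 × 0.5^6 = 0.031

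With 12 per arm (6.2), six such moves are enough for p < 0.05. The documents do not say how likely a move is. Assume that all 12 patients are untreated and at 'response' at baseline, and that each moves with probability q. Then P(6 or more of 12) is:

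| q (assumed) | P(at least 6 moves) |
|---|---|
| 0.3 | 0.12 |
| 0.4 | 0.33 |
| 0.5 | 0.61 |
| 0.6 | 0.84 |

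If fewer than 12 are untreated, the chance of six such moves is smaller at the same q.

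**4. The total.** Suppose starting a rinse raises side-effect concern by s, limits by l and satisfaction by t (mean points, assumed). If satisfaction is reverse-scored so that higher is worse throughout, the total shifts by s + l − t. If it is summed as printed, the shift is s + l + t. The plan has no reverse-scoring rule.

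- s = l = t = 1: 1 + 1 − 1 = +1 reversed, or 1 + 1 + 1 = +3 as printed
- s = l = 1, t = 2: 1 + 1 − 2 = 0 reversed
- s = l = 1, t = 3: 1 + 1 − 3 = −1 reversed

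The sign under correct scoring therefore depends on quantities the documents do not give.

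**The case against.** Section 3.2.1 excludes only patients on steroids. Other treatment for oral lichen planus at entry is not excluded, no washout is stated, 5.5 leaves concomitant medication unrestricted, and the printed form gives no recall period. Some patients may therefore rate a current or past treatment at baseline. This stands: the problem applies to patients untreated at visit 1, and their share is unknown. A reader might infer that the design forces every patient to 'not at all' on the limits item, so that no one can improve. The documents do not support that.

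A reader might also infer that the total understates improvement. That does not follow. Correctly scored, a patient who starts at 'not at all' satisfied can only improve on that item, which offsets the burden items.

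Nor do all three items lack a baseline. Patients are told the risks at consent (4.1), so side-effect concern can be answered then and may fall by week 4.

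Rinse tolerability is also captured elsewhere: comfort and taste on the Visit 2 form, adverse effects in the diary, and toxicity. Week-4 COMDQLQ values are summarised by arm, so they are not ignored. The wording of 2.3 is at best ambiguous on whether the COMDQLQ is meant to measure tolerability of the rinse.

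Finally, limitation caused by a rinse is a real burden. That is a reason to report the items, and it is best served by comparing the arms. It does not make within-arm change a measure of disease response.

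**Conclusion.** The point holds in a limited form. For patients untreated at baseline, within-arm change and McNemar results on the satisfaction and limits items, and in part on the side-effect item, cannot separate the start of a rinse from change in disease. Six one-way moves in an arm of 12 would give p = 0.031 on the limits item. That is an assumed scenario, and the chance of reaching it runs from 0.12 to 0.84 over assumed move rates of 30% to 60%. The three items carry 12 of the 104 printed points, and the net direction of their effect on the total is unknown.

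The mismatch of 24 and 26 items is certain but minor. The same form is used at both visits, so change can be computed, but the items in the total are not fixed. The issue is confined to a secondary endpoint. The primary endpoint and the sample size are unaffected.

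**What to change.** In 6.5:

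1. State that within-arm pre-to-post and McNemar tests of the three medication-in-use items will not be interpreted as treatment response.
2. Compare the week-4 values of those three items between arms. The t-test or Mann-Whitney choice already given for the REU score would serve.
3. Report change in the total with and without the three items. On the printed form that is 26 items (maximum 104) and 23 items (maximum 23 × 4 = 92).
4. Reconcile the 24 items in 5.1.2, 6.1 and 6.5 with the 26 printed in Appendix 5. List the items that form the total and say how the satisfaction item is scored.

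This takes a few sentences and no new data. The small downside is one extra summary score beside the full total. It should be settled before analysis, so that the choice of score is not made after seeing the results.
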